	III. Questionnaires	

STUDY TEAM ROSTER

1. [name]

Email: [contact]

Ph: [name]

Lab:[name]

[contact]

[contact]

Snail Mail: Graduate School of Creative Arts Therapies

[name]

University of Haifa

[name]

[name]

2. [name]

Email: [contact]

Ph: [contact]

[contact]

Snail Mail: Department of Psychiatry

College of Medicine

University of Arizona

[name]

[name]

3. [name]

Email: [contact]

Ph: [name]

[contact]

Snail Mail: [name]

University of Arizona

[name]

4. [name]

Email: [contact]

Ph: [contact]

[contact]

Snail Mail: Monash Institute of Cognitive and Clinical Neurosciences

School of Psychological Sciences

Monash University
[name]
[name]

5. [name]

Email: [contact]
Ph: [name]
Snail Mail: [name]
University of Haifa
[name]

[name]

6. [name]

Email: [contact]
Ph: [name]
[contact]
Snail Mail: [name]
University of Haifa
[name]

[name]

7. [name]

Email: [contact]
Ph: [name]
Snail Mail: [name]
University of Haifa
[name]

[name]

8. [name] PhD

Professor of Psychiatry, Psychology and Neuroscience
Ph: [contact]
[contact]
Snail mail: [name]
University of Arizona
[name]

PARTICIPATING STUDY SITES

1. Rambam Medical Center

[name]

Email: [contact]

Ph: [name]

[contact]

Snail Mail: [name]

[name]

2. Rabin Medical Center

[name]

Email: [contact]

Ph: [name]

[contact]

Snail Mail: Beilinson Hospital,

[name]

[name]

3. Ziv Medical Center

[name]

Email: [contact]

Ph: [name], [name]

[contact]

Oncology Institute

[name]

[name]

Study Title

REPAT- Role of Emotional Processing in Art Therapy for Breast Cancer Palliative Care Patients: A Mechanistic Study

Objectives

The purpose of this study is to examine two mechanistic changes: emotion processing (awareness, expression and acceptance) and cholinergic anti-inflammatory processes (HRV and cytokine expression) through which an Art Therapy (AT) intervention reduces depression, pain and fatigue.

Design and Outcomes

For this means, we have designed a randomized controlled study with careful controls. Our study population is comprised of 240 BC patients in palliative and curative care (comprised of 50% Jewish and 50% Arab). This population will be randomized (using a permuted block design to account for ethnicity and level of traditionalism) to receive a standard art therapy intervention or a comparison group. The intervention is designed to increase emotion processing via art making in a supportive environment. The sham Art Therapy comparison group will engage in the coloring of prefabricated shapes (mandalas) and will receive Psychoeducation on topics related to coping with BC, identical to the topics of the AT group. This design will allow the study to test the mechanism of AT that is beyond the effects of time with a group, focus on a task and engagement with art materials.

Interventions and Duration

The AT intervention is an 8-week group intervention comprised of 8 1.5-hour weekly sessions conducted by an experienced Art Therapist who received special training in conducting the treatment protocol as designed. The intervention and comparison group were piloted on BC patients at Beilinson hospital and the protocol was modified based on feedback from the participants. Each intervention module is described below.

The comparison group will be an 8-week group intervention comprised of 8 1-hour weekly mandala coloring sessions with a self-care educational component, conducted by someone with experience conducting groups who will be trained in providing a well-planned comparison group, with fidelity checks that includes coloring pre-fabricated mandalas.

There will be an additional follow up time point 8 weeks after the intervention is over to assess

the lasting effects of the intervention.

Sample Size and Population

240 BC survivors will be randomized to the intervention and comparison groups. We are targeting 300 women and expect an attrition rate of 15%. We also will be targeting the recruit of 50% of our sample to be of Arab origin and 50% Jewish.

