The comparison group will meet for a half an hour. The interventionist will encourage the participants to color prefabricated shapes for 30 minutes. The same art materials as in the intervention group will be on the table as will the same instrumental music. We will not be controlling for the whole 90 minutes of the intervention group as are concerned that comparison group participants will become bored and this will defeat the purpose of the comparison group. The detailed role of the interventionist is described in section 5.2, and it is tailored to ensure optimal opportunities for participants to engage in emotional processing in a supportive environment.

The interventionists of both groups will keep scores that will be rated by the PI against the treatment manual to ensure fidelity (see Table 2).

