Session 2: Art making will be exploratory in the framework of open studio in which a specific topic is not provided and participants are encouraged to explore the art materials. The goal of this session is to provide an experiential encounter with the art making process. There will be a 10-minute Psychoeducation presentation on the nature of emotions at the beginning of the session.

Session 3: Group members will introduce themselves to the group by making a drawing about an emotion. The goal of this session is to continue learning on the nature of emotions and increase awareness of emotion responding patterns.

Session 4: The art therapist requests the participants to create an image of somethings that is distressful to them and sit with it for a while. Then, they are requested to create an additional drawing that changes one element of the distress drawing, a feature, a color, a shape, or just a change in composition. The images are discussed among group members and implications for real life situations are discussed. The goal of this session is twofold- to identify the location of distress in the body, increase distress tolerance, cognitive flexibility and reframing.

Session 5: This session is open studio in which participants are encouraged to engage freely with the art materials. The goal of this session is to help participants identify how they react and respond to their emotions and bring an awareness of emotional experiences and learn the skill of "Clearing the Space"-using artmaking to identify feelings and experiences without the need to identify with them.

Session 6: Clients are requested to draw two sides of a current conflict in their life. It can be something small, like deciding where to go for lunch, or something large, like which treatment to

engage in. All conflicts are welcome, but it should have significance to its creator and be something that they are struggling with and would like to learn more about. After the drawing period, clients are requested to look at both options and examine their sensations, feelings and thoughts about each. Their art, thoughts and feelings are shared with the group. The goal of this session is to increase cognitive flexibility and reframe. This means that through creating 2 pictures participants will be able to view a situation from 2 points of view and identify more than one option for coping with the conflict they presented.

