Session 7: Body image: In this module participants will create art using body outline templates as a framework for art making. The goal of this session is to increase introceptive awareness and assist in processing emotional content from implicit experience to explicit expression. Distress tolerance.

Session 8: Summary: This session will be a summary of all that has been experienced and clients will be provided with a letter that summarizes their progress. Each client will receive a package of oil pastels and blank journal for the encouragement of their continued process at home. The goal of this session is to review achievements and encourage incorporating what was learned in day to day life after the intervention is over.

The comparison group is designed to control for the impact of the aspect of the group experience that are not explicitly focused on emotional processing, ie, the time with art materials and focused attention aspects that occur during an Artmaking session. These sessions will not have a rapport building component and will include 40 minutes of coloring pre-fabricated shapes (Mandalas- see figure 3) in a calm environment and 20 minutes of self-care instruction. Coloring Mandala's has been demonstrated to reduce anxiety⁶⁸⁻⁷⁰. Participants are encouraged to minimize conversation; instrumental music is played to encourage introspective experiences. Due to our concerns that participants will become bored after more than 40 minutes of coloring we will not be equally comparing the amount of time that participants are together in the group format.

Figure 3: Mandala example

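### The synopsis claims the design rules out group contact time, but contact is unequal by design (720 vs 480 minutes, or 240 under a conflicting passage) and cannot be separated from arm

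*Protocol*

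**What the plan says.** The synopsis (Design and Outcomes) states the purpose of the comparator: "This design will allow the study to test the mechanism of AT that is beyond the effects of time with a group". The same sentence adds focus on a task and engagement with art materials. It also says the comparator receives "Psychoeducation on topics related to coping with BC, identical to the topics of the AT group".

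The synopsis then sets the doses (Interventions and Duration). For AT: "The AT intervention is an 8-week group intervention comprised of 8 1.5-hour weekly sessions". For the comparator: "8-week group intervention comprised of 8 1-hour weekly mandala coloring sessions with a self-care educational component". Section 5.1 repeats an hour and a half against one hour. Section 5.2 divides the comparator hour into 40 minutes of colouring and 20 minutes of self-care instruction, with no rapport-building. Section 3 instead has the comparator meeting for half an hour, all of it colouring.

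Two sections say outright that time is not matched. Section 3: "We will not be controlling for the whole 90 minutes of the intervention group". Section 5.2: "we will not be equally comparing the amount of time that participants are together in the group format". The reason given in both is concern about boredom.

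On education in the AT arm, Section 5.2 describes one item, in Session 2: "There will be a 10-minute Psychoeducation presentation on the nature of emotions at the beginning of the session". Session 3 continues the theme as a learning goal.

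SAP C.5.2 tests the mechanisms by a Time × Condition interaction. It tests mediation by the product of path a (Condition to change in mechanism) and path b (change in mechanism to change in symptoms).

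**The concern.** This is presented as a mechanistic study, so the main inference depends on what the comparator holds constant. A factor that differs between arms by design is not held constant. If an extra four to eight hours of group contact, or the rapport component, improves emotion processing, HRV, cytokines or symptoms, the trial would show an arm difference that the synopsis invites the reader to credit to the AT mechanism.

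The primary outcomes are the mechanisms themselves, so the problem applies first to the Time × Condition tests. It then carries into mediation: contact that raises a mediator, which in turn lowers symptoms, appears as an indirect effect.

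**Working it through.** **1. Do the stated session lengths add up?** AT (Sections 3 and 5.2): 10 + 50 + 30 = 90 minutes, which agrees with 1.5 hours. Comparator (Section 5.2): 40 + 20 = 60 minutes, which agrees with one hour in the synopsis and Section 5.1. The half hour in Section 3 fits neither the 40 + 20 split nor any education component.

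**2. Total contact over eight sessions.**
- AT: 8 × 90 = 720 minutes (12 h).
- Comparator, one-hour version: 8 × 60 = 480 minutes (8 h). Ratio 480/720 = 0.67; difference 240 minutes.
- Comparator, half-hour version, assuming eight sessions: 8 × 30 = 240 minutes (4 h). Ratio 240/720 = 0.33; difference 480 minutes.

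**3. Where the difference lies, in minutes per session.** The components sum to the total gap, so they must not be added to it.

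| Component | AT | One-hour comparator | Gap | Half-hour comparator | Gap |
|---|---|---|---|---|---|
| Rapport | 10 | 0 | +10 | 0 | +10 |
| Art or colouring | 50 | 40 | +10 | 30 | +20 |
| Discussion | 30 | none described | +30 | none described | +30 |
| Self-care instruction | 0 | 20 | −20 | 0 | 0 |
| Total | 90 | 60 | +30 | 30 | +60 |

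The fidelity form in Section 5.4 uses a 10/60/20 split for AT. That moves 10 minutes from discussion to art making and leaves the totals unchanged.

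**4. Education.** Comparator (Section 5.2): 8 × 20 = 160 minutes on self-care. AT: one 10-minute talk on emotions. The self-care topics are not listed, so the comparison rests on these descriptions alone.

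**5. Can analysis repair it?** Contact per session is fixed by arm. A planned-contact covariate would be an exact function of Condition, so the two cannot be estimated separately.

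**6. What could be at stake (illustration).** The documents give 120 per arm but no significance level; I assume two-sided 0.05, independent observations and a simple comparison of two means. P(significant) = Φ(d√(120/2) − 1.96) + Φ(−d√(120/2) − 1.96). At d = 0.50 this gives 0.97, consistent with the stated power above 90%. Now suppose the specific mechanism has no effect and extra contact alone produces an effect d:
- d = 0.1: 0.12
- d = 0.2: 0.34
- d = 0.3: 0.64

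Without any contact effect the figure is 0.05. These values of d are assumptions; the documents give no estimate of a contact effect.

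**7. Role of the direct path.** Suppose Condition affects symptoms by a route c′ outside the mediator, and Condition is left out of the symptom equation. Path b is then biased by c′ × Cov(M, X)/Var(M). With equal arms, the planning effect of 0.50 on the mediator and within-arm SD 1, the factor is (0.50 × 0.25)/(1 + 0.50² × 0.25) = 0.125/1.0625 = 0.118. For c′ of 0.1 to 0.3 the bias is about 0.01 to 0.04. It is modest and avoidable. Including Condition removes it, but leaves untouched any contact effect that passes through the mediator.

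**The case against.** The protocol discloses the unequal time twice and gives a reasonable reason. That is correct, and nothing is hidden. But the disclosure in Sections 3 and 5.2 leaves the contrary statement standing in the synopsis.

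A stronger defence is that the extra time is the active ingredient. Section 2.2 describes emotional expression as mainly verbal, Section 2.4 makes discussion of the art part of AT, and Section 5.2 limits the comparator to aspects not explicitly focused on emotional processing. A reader might infer that the absence of discussion in the comparator is itself a flaw; the documents do not support that, because it is the intended contrast. Under the one-hour version, AT without discussion also lasts 10 + 50 = 60 minutes, equal to the comparator. This defence does not rescue the claim about group time: the added discussion is also added group time, so an effect beyond group time cannot be shown. Rapport-building is unmatched in either version.

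The sentence in the synopsis also names task focus and art materials. The comparator does address these, with 40 against 50 minutes of art activity in the one-hour version, and it provides a group setting. Section 8.1 claims only shared art materials and group setting, so it needs little change.

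Finally, the path diagram for Hypotheses 1 and 2 is not available in the text reviewed and may already contain the direct path. Its absence cannot be assumed.

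**Conclusion.** The synopsis states a property the design lacks. Comparator contact is two-thirds of AT contact under the synopsis and Sections 5.1 and 5.2. It is one-third under Section 3 alone, if that version also meets eight times. Contact time and rapport are aliased with arm and remain alternative explanations for the mechanism outcomes and the indirect effects. The comparator's partial control for group setting, task focus and art materials stands.

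Three stronger readings go too far.
- A reader might infer that the education topics are shown to differ. The self-care topics are not listed; the session descriptions fail to substantiate "identical to the topics of the AT group", but they do not prove it false.
- A reader might take one-third as the plan's figure. It rests on a single passage that conflicts with the others.
- A reader might infer that any contact effect on symptoms is a direct effect, so that a direct path in the model would isolate emotional processing. Contact that raises a mediator acts indirectly, and the direct path cannot remove it.

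The contact arithmetic rests on the documents plus the eight-session assumption for the half-hour version. The probabilities in the working are illustrations only. The stated power figures are not affected.

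**What to change.** Keep the design and change the text.

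1. In the synopsis (Design and Outcomes), take group time out of the list of features the design is said to rule out. State that contact time and rapport are aliased with arm and remain alternative explanations for both the mechanism outcomes and the indirect effects.
2. Reconcile the half-hour comparator session in Section 3 with the one-hour session in the synopsis and Sections 5.1 and 5.2.
3. Reconcile the statement on identical psychoeducation topics with the session descriptions in Section 5.2, for example by listing the topics for each arm.
4. In SAP C.5.2, state that Condition is a predictor in the symptom equation of each mediation model, unless the path diagram already shows it. Say that this guards path b against confounding by arm and does not separate contact time from emotional processing.

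The cost is a less favourable stated inference and one explicit model term. Sample size and the randomised comparison are unchanged.

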1. STUDY OBJECTIVES

To examine two mechanisms: 1) emotional processing (awareness, acceptance and expression) and 2) cholinergic anti-inflammatory processes (resting HRV and inflammatory cytokines), through which AT reduces depression, pain and fatigue in Arab and Jewish BC survivors.

To examine ethno-cultural differences in the effect of Art Therapy in women from a traditional collectivist ethno-cultural background, in comparison to women from a more individualist western ethno-cultural background.

2. BACKGROUND AND RATIONALE

2.1 Background on Condition, Disease, or Other Primary Study Focus

Over 200,000 women are diagnosed with breast cancer (BC) in the United States annually¹. As of January 1, 2016 there were 3,560,570 breast cancer survivors in the United States². Cancer survivorship is defined as living with the challenges that occur as the result of a cancer diagnosis and treatment³. Thus, in this document patient and survivor are used interchangeably.

Many breast cancer patients cope with depression. Stress and negative emotion are normative responses to cancer diagnosis and treatment, but approximately one-third of individuals coping with cancer experience the debilitating consequence of depressive disorders⁴ which have been linked with functional limitation in survivorship⁵. Depressive symptoms are persistently elevated in the year following cancer diagnosis; 38% of BC survivors experience depressive symptoms in the clinical range^{6,7}. These individuals suffer more physical symptoms, problems with treatment adherence, functional limitation in survivorship⁶ and increased mortality⁸.

There are several physical symptoms that occur commonly in BC survivors. Pain and fatigue are some of the most prominent symptoms that affect quality of life (QoL) and well-being of cancer survivors. A reported 25% to 60% of women develop chronic pain after BC treatment and chronic fatigue is reported in between 30-60% of survivors^{3,8,9}. **Physical symptoms co-occur with distress and are very difficult to treat.** Cancer survivors with high symptom burden suffer from diminished QoL, which compromises physical, psychological and social functioning⁶.

2.2 Emotion processing has been associated with improved physical and psychological health in BC survivors. **Emotion processing** is comprised of 1) emotional awareness, 2) expression, and 3) acceptance. Increased **emotional awareness** occurs when knowledge is transferred from sensorimotor or bodily information to patterns of explicit thought that include conscious processing through language or other symbolic formations, such as visual art¹⁰⁻¹². Low levels of emotion awareness were found in individuals with somatoform disorders¹³. **Emotional**

expression refers to the extent to which feelings are intentionally¹⁴ (mainly verbally) and non-intentionally¹⁵ (body language, facial expressions) conveyed to others. Increased emotion expression and reduced avoidance have long been associated with improved wellbeing¹⁶⁻¹⁹. Increased emotional expression is associated with improved psychological and physical adjustment to BC²⁰⁻²³. **Acceptance of emotion** is an emotion regulation strategy in which individuals embrace an attitude of being accepting, friendly, and nurturing toward their feelings^{19,24}. Acceptance of emotion has been associated with experiencing less fear, catastrophic thoughts, avoidance behavior and better recovery from negative affect as compared to suppression²⁵. Women coping with BC who were less accepting of their emotions also reported greater distress²⁶ and sickness symptoms²⁷.

2.3 There are ethno-cultural differences in response to cancer diagnosis. Women from traditional backgrounds, in which there is an emphasis on collectivism as opposed to individualism and a reliance on religion as a major coping strategy, may respond differently to cancer diagnosis and treatment than do more modern/secular women. Women from traditional backgrounds may see cancer diagnosis as fate and fear stigma related to exposing their diagnosis²⁸. Furthermore, out of fear of their loss of role in the traditional family, women may not express their distress openly, which leaves them at risk for loneliness and not receiving help for their symptoms²⁸⁻³⁰. BC survivors from ethnic minorities report poorer social, emotional, spiritual and physical quality of life³¹. Since expression of emotion and venting is distressing for some ethnic minorities^{32,33}, art making and the use of metaphors as a form of emotion processing may be less distressing and more helpful in reducing symptoms and increasing quality of life^{34,35}. Israel is a multi-cultural country with differences between the Jewish and Arab population. Israeli Arabs of different subgroups in comparison to Israeli Jews were found to be more conservative and hierarchical, and less autonomous³⁶⁻³⁸.

2.4 Art Therapy interventions encourage emotion processing. Art therapy is a form of psychotherapy that involves the use of visual art-making (drawing, painting, sculpting, collage, etc.) for expression and communication within a safe and supportive relationship, in a therapeutic setting³⁹. The Art Therapy session includes (i) an introductory period in which the therapist engages with participants to establish rapport and begins to understand participants' current state of mind, (ii) an art making period which entails much of the time, and (iii) a processing period in which the art made is looked at and discussed. Art Therapy has been well documented in cancer settings to alleviating psychological symptoms and reducing physical complaints⁴⁰⁻⁴⁴. In a qualitative study, women with breast cancer reported that art making was helpful through increased access to emotional content and its expression⁴⁵.

We hypothesize that increased Emotion Processing is a primary mechanism through which Art Therapy effects psychological and physical symptom reduction in breast cancer patients.

2.5 Heart rate variability and inflammation are related to emotion processing and depression, anxiety, fatigue and pain.

The **cholinergic anti-inflammatory pathway** is comprised of vagus nerve signals leading to acetylcholine-dependent interaction with the alpha 7 nicotinic acetylcholine receptor subunit (a7nAChR) on monocytes and macrophages, resulting in reduced cytokine production⁴⁶. Vagal modulation is related to physiological adaptability and emotional regulation⁵³. Decreased vagus nerve activity and the associated loss of the tonic inhibitory influence of the cholinergic anti-inflammatory pathway on innate immune responses and cytokine release, are hypothesized to pathologically enhance cytokine responses to stimuli, such as psychological stress⁴⁷. **Heart rate variability** (HRV) is a measure of beat-to-beat temporal changes in heart rate and these changes reflect the output of the central autonomic network. The vagus nerve is a core component of the parasympathetic nervous system (PNS) within the central autonomic network and it regulates metabolic output in response to environmental stimuli and enables social engagement⁴⁸. HRV can encompass both Sympathetic nervous system and PNS influences, but our primary interest is on the PNS influences, and at rest, a majority of HRV is related to PNS influence. In reviewing the literature, which reports a wide variety of metrics, we will use the more general term HRV, whereas our specific hypotheses will involve the subset of HRV that is specifically linked to PNS influence: high frequency (HF) HRV that reflects respiratory sinus arrhythmia (RSA)⁴⁹.

The **neuro visceral-integration model** views psychopathology such as anxiety being 'stuck' in a behavioral pattern that is not responsive to the demands placed upon it by the environment^{54 50} and asserts that lower HRV is associated with poor health because it reflects excess allostatic load as indexed by excess **pro-inflammatory cytokines**⁴⁷. High levels of **pro-inflammatory cytokines and low HRV are related to depressed mood, fatigue and pain** in cancer patients⁵¹⁻

⁵⁴

Low HRV has been linked to difficulties in emotion regulation⁵⁵⁻⁵⁷ in the prediction of anxiety in BC patients⁶², and reports of sadness and crying in depressed individuals^{58,59}. Disrupted nocturnal sleep was related to lower HRV the following day along with a flattened diurnal cortisol rhythm in women with metastatic BC^{60,61}.

